12.1.3. Recording Adverse Events

AEs will be recorded in source documents and entered into the eCRF and must indicate clearly the event being assessed.

12.1.4. Reporting Serious Adverse Events

Any SAE, including death resulting from any cause, which occurs to any subject participating in this study or within 30 days following cessation of the study treatment or premature discontinuation from the study whether or not related to the investigational product, must be reported via facsimile or telephone within 24 hours of first being advised of the SAE. Follow-up information collected for any initial report of an SAE must be reported to the sponsor within 24 hours of receipt by the Investigator. In the event discussion is necessary regarding treatment of the subject, the Investigator should call the Medical Monitor.

All SAEs should be submitted to Endo Pharmaceuticals, [REDACTED]
[REDACTED]
[REDACTED]

The Sponsor will determine whether the SAE must be reported within 7 or 15 days to the FDA. If so, the Sponsor (or the Sponsor's representative) will report the event to the FDA. The Investigator will transmit a written report of the circumstances and outcome to the Sponsor as soon as he/she is made aware of the circumstances. The Investigator will report all SAEs to the IRB.

12.1.5. Overdose/Misuse/Abuse

12.1.5.1. Overdose

Study drug overdose is any accidental or intentional use of study drug in an amount higher than the dose indicated per protocol for a given subject. Study drug compliance (see section 9.7) should be reviewed to detect potential instances of overdose (intentional or accidental).

Any study drug overdose during the study should be noted on the study drug eCRF.

All AEs associated with an overdose should both be entered on the Adverse Event eCRF and reported using the procedures detailed in section 12.1.4, even if the events do not meet seriousness criteria. If the AE associated with an overdose does not meet seriousness criteria, it must still be reported using the Endo Clinical Trial Report Form for SAEs and in an expedited manner, but should be noted as non-serious on the form and the Adverse Event eCRF.

12.1.5.2. Misuse/Abuse

Adverse events associated with misuse or abuse will be appropriately reported as AEs or SAEs, and monitored per section 12.

12.1.6. Pregnancy

Any uncomplicated pregnancy that occurs during this clinical study will be **reported for tracking purposes only**. All pregnancies that are identified during or after this study, where the estimated date of conception is determined to have occurred within 14 days or 5 half-lives (whichever is longer) after exposure to study drug need to be reported, followed to conclusion, and the outcome reported, even if the subject is discontinued from the study. Pregnancies that occur in the partner of a treated subject (ie, female partner of male subject) also need to be reported. The Investigator should report all pregnancies within 24 hours using the Initial

Pregnancy Report Form, and any pregnancy-associated SAE using the SAE report form, according to the usual timelines and directions for SAE reporting provided in section 12.1.4. Monitoring of the pregnancy should continue until conclusion of the pregnancy; 1 or more Follow-up Pregnancy Report Form(s) detailing progress, and a Two-Month Follow-up Pregnancy Report Form detailing the outcome, should be submitted.

Pregnancy itself is not regarded as an AE unless there is suspicion that the investigational product under study may have interfered with the effectiveness of a contraceptive medication. Likewise, elective abortions without complications are not considered AEs. Any SAEs associated with pregnancy (eg, congenital abnormalities/birth defects/spontaneous miscarriages or any other serious events) must additionally be reported as such using the SAE report form. Spontaneous miscarriages should also be reported and handled as SAEs.

Subjects should immediately notify the Investigator of any pregnancies.

A subject who becomes pregnant must be withdrawn from the study. Should a subject discontinue treatment due to pregnancy, alternative treatment (if available) should be arranged according to standard of care, as determined by the Investigator.

12.1.7. AEs/SAEs Experienced by Non-Subjects Exposed to Study Drug

Non-subjects exposed to study drug are persons who are not enrolled study participants, but have been exposed to study drug, including instances of diversion of study drug. All such AEs/SAEs occurring in association with such exposure will be recorded on the Endo Pharmaceuticals Inc. Clinical Trial Report Form for SAEs/AEs of special interest. All events occurring in non-subjects exposed to study drug will be processed within the same SAE reporting timelines as described in section 12.1.4.

12.2. Assessments of Respiratory Function

In children, a rare, but well known, side effect of all opioids is respiratory depression. In this study, all subjects will be monitored for the appearance of the following respiratory symptoms not only at the time of scheduled assessments, but as needed throughout the study duration through the aid of respiratory monitoring equipment:

- Oxygen saturation and heart rate will be monitored using a pulse oximeter. Oxygen saturation and heart rate will be recorded at the time of vital sign assessment. If oxygen saturation decreases to $\leq 90\%$, the event will be recorded as an AE at the discretion of the Investigator. If the heart rate decreases to $\leq 50\%$ of the expected norm for age, the event will be recorded as an AE at the discretion of the Investigator. NB. Bradycardia for age may be indicative of hypoxia in children; tachycardia for age may be indicative of inadequate analgesia in children.
- If the respiration rate decreases to $\leq 50\%$ of the expected norm for age, the event will be recorded as an AE of respiratory depression at the discretion of the Investigator.

- Apnea monitoring may be conducted using direct observation and counting, impedance pneumography, or capnography, based on practice at the respective institution. Apnea may be defined as a cessation of respiration for a period of ≥ 15 seconds. Episodes of apnea will be recorded as an AE at the discretion of the Investigator (or an SAE per respective definition in the safety section of the protocol [see section 12.1.2]).
- Any administration of an opioid antagonist (eg, naloxone) to treat respiratory depression will be recorded as an SAE per definition in section 12.1.2.

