12.6. Vital Signs

Vital signs (respiratory rate, body temperature, heart rate, and blood pressure) will be taken at the screening visit, pre- or intraoperatively, at baseline, and at each specified time point during the Single- and Multiple-Dose Phases (see [Table 3](#) and [Table 4](#)). Blood pressure should always be taken in the same arm and when the subject has been supine for 5 minutes.

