13.5. Safety and Tolerability Analysis

Assessment of safety and tolerability will be based on the incidence of AEs, AEs resulting in discontinuation, and SAEs. Adverse events will be coded using the Medical Dictionary for Regulatory Activities (MedDRA). Summaries of AEs will be provided showing the number and percentage of subjects who experience at least 1 AE. These summaries will be presented by system organ class and preferred term. The occurrence of AEs will also be tabulated by severity. SAEs and AEs resulting in discontinuation will be summarized separately.

Assessment of safety and tolerability will also be based on pharmacokinetic analysis (described in section 13.6) clinical laboratory results, vital sign measurements, respiratory and neurological assessments, and other safety variables, which will be summarized by age group, treatment cohort, and study phase for each time point using appropriate descriptive statistics.

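### Oxygen saturation is recorded and summarised by cohort with no specified record of inspired oxygen beside each reading, so the saturation data cannot be fully interpreted or compared

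*Combined protocol and SAP*

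**What the plan says.** Section 12.2 has saturation monitored by pulse oximeter, and "Oxygen saturation and heart rate will be recorded at the time of vital sign assessment". A fall to 90% or below is to be recorded as an adverse event at the Investigator's discretion. The threshold is the same whatever the child is breathing.

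Section 12.6 defines the vital signs: "Vital signs (respiratory rate, body temperature, heart rate, and blood pressure) will be taken at the screening visit". It has no oxygen-delivery item. Tables 3 and 4 schedule respiratory assessments alongside vital signs and add none either.

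Section 13.5 covers respiratory assessments among the safety variables, "which will be summarized by age group, treatment cohort, and study phase for each time point using appropriate descriptive statistics". It makes no split by oxygen status. Under section 7 the IDMC reviews individual and aggregate safety data before each escalation, on six children per age group and cohort.

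Section 12.2 does not rely on saturation alone:
- When respiratory rate falls to half the age norm or less, "the event will be recorded as an AE of respiratory depression at the discretion of the Investigator".
- Episodes of apnea can be recorded as adverse events, with the monitoring method left to each site.
- Reversal of respiratory depression carries no discretion clause: "Any administration of an opioid antagonist (eg, naloxone) to treat respiratory depression will be recorded as an SAE".

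Section 12.3 adds sedation scoring by each institution's own practice.

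**The concern.** A saturation value on room air and the same value on oxygen are different measurements. Supplemental oxygen can hold saturation up while ventilation falls, and oxygen given because a child is hypoventilating makes the recorded number look better. The subjects are post-operative inpatients coming off parenteral opioids at about 20 centres, so it is reasonable to infer that some will be on oxygen at some readings and that practice will vary by site.

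Cohorts are enrolled in sequence and without randomisation, so nothing in the design balances oxygen use between dose levels. A cohort with more oxygen use could show higher saturations for that reason alone, and the planned summaries would give no means of seeing it. Oxygen status at each reading could not be reliably reconstructed afterwards. At stake is how far the IDMC and the final report can rely on one of the respiratory measures reviewed before escalation.

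**Working it through.** **1. Is oxygen status captured?** The plan gives no figure on this point to reproduce, so the first check is of the text. Apart from saturation in section 12.2, oxygen appears only in the abbreviation list. Sections 7.1.1 to 7.1.6, 12.2, 12.6 and 13.5 and Tables 3 and 4 contain no item for room air, device, flow or inspired fraction. Three general rules could pick up some oxygen use:
- Section 9.3 records concomitant medications with dose, date and time, and section 13.3.3 tabulates them. Oxygen is not named.
- Section 12.1.2 requires the treatment given for each adverse event to be recorded.
- Section 7.1.8 requires interventions, including non-pharmacological ones, to be documented.

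None ties oxygen to a saturation reading or to the saturation summary. The last two arise in connection with adverse events, so they may not operate if a masked reading prompts no event. Appendix B, which governs medication capture, was not in the text reviewed.

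**2. How far can oxygen shift the 90% point?** The only input from the documents is 90%. Assumed: 760 mmHg barometric pressure, 47 mmHg water vapour, respiratory quotient 0.8, normal PaCO2 40 mmHg, alveolar-arterial gap 10 mmHg (range 0 to 20), 90% saturation taken as PaO2 60 mmHg, and constant CO2 production.

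Alveolar PO2 = FiO2 × 713 − PaCO2/0.8. Setting this to 60 + gap gives PaCO2 = 0.8 × (713 × FiO2 − 60 − gap). The fall in alveolar ventilation is 1 − 40/PaCO2.

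| FiO2 | PaCO2 at 90%, gap 10 | Ventilation fall | Range, gap 20 to 0 |
|---|---|---|---|
| 0.21 | 0.8 × (149.73 − 70) = 63.8 | 37% | 28–44% |
| 0.25 | 0.8 × (178.25 − 70) = 86.6 | 54% | 49–58% |
| 0.30 | 0.8 × (213.90 − 70) = 115.1 | 65% | 63–68% |

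**3. The same hypoventilation, different readings.** With gap 10 and the saturation curve S = 100/(1 + 23400/(P³ + 150P)), where P is PaO2 in mmHg:

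| PaCO2 | Room air | FiO2 0.24 | FiO2 0.28 |
|---|---|---|---|
| 70 | 86.5% | 94.6% | 97.9% |
| 80 | 74.6% | 91.0% | 96.9% |

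Both rows meet the 90% prompt on room air and miss it at either oxygen level.

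**4. Would the respiratory-rate prompt catch it?** Suppose the fall is entirely in rate, at constant tidal volume and starting from the age norm. A 37% fall leaves 63% of norm, so on room air saturation reaches its prompt before rate does. Falls of 54% and 65% leave 46% and 35% of norm, so on oxygen the rate prompt (50% or less) comes first. Under these assumptions, falls between 37% and 50% meet the saturation prompt on room air but meet neither prompt at 25% or 30% oxygen. If the fall is mainly in tidal volume, the rate prompt helps less.

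**5. Effect in a cohort of six.** The chance that at least one child shows an event is 1 − (1 − p)⁶. The true rate p and the masked share are both assumed.

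| True rate | None masked | Half masked |
|---|---|---|
| 10% | 0.47 | 0.26 |
| 20% | 0.74 | 0.47 |
| 30% | 0.88 | 0.62 |

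At a 20% rate, masking 25% or 75% of events gives 0.62 or 0.26.

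**The case against.** The strongest reply is that the plan has several respiratory safeguards that do not depend on inspired oxygen: respiratory rate, apnea, sedation and antagonist use. Step 4 shows that the more extreme masked falls would meet the rate prompt if they were rate-driven. The 90% value is a discretionary prompt, and an Investigator at the bedside can take oxygen into account. Section 13.5 is descriptive and plans no explicit count of readings at or below 90%. The IDMC sees individual data on six children, not only means. Oxygen may also be logged under the general rules or Appendix B. Splitting cohorts of six leaves very small cells.

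Most of this stands, and it rules out several readings that a reader might infer:
- **That respiratory depression would go undetected.** The parallel measures prevent that conclusion. They are imperfect: the rate and apnea events are discretionary, the apnea method is left to the site, and after Dose 1 in the Multiple-Dose Phase the scheduled respiratory readings are only pre-dose or at end of study (section 7.1.5).
- **That the cohorts are not comparable.** Nothing in the documents shows oxygen use differing by dose. What can be said is that comparability of saturation cannot be checked.
- **That oxygen is never recorded or summarised.** Some use may be recorded, and may reach the medication tables, without a link to readings.
- **That saturation is formally tested against 90%.** It is not.

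The reply does not make a saturation table interpretable. Individual review does not help with an item that the plan does not require with the reading.

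**Conclusion.** The concern holds for the saturation measure. As specified in the text reviewed, readings on room air and on oxygen are pooled, the hypoventilation signal in saturation can be blunted, and its comparability across cohorts cannot be verified.

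Under the stated gas-equation assumptions, the ventilation fall needed to reach 90% moves from about 37% on room air to 54% at 25% oxygen and 65% at 30%. That is a physiological possibility and not an estimate of bias in this trial: the documents give neither the frequency of oxygen use nor its distribution by cohort. The cohort-of-six probabilities are likewise illustrations on assumed rates. The conclusion also assumes that Appendix B does not already require oxygen status with each reading, which should be checked first.

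**What to change.** Add one eCRF item to every existing saturation reading in Tables 3 and 4: room air, or supplemental oxygen with flow or inspired fraction. Name it in section 12.2.

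In section 13.5 and the IDMC listings:
- show saturation, and readings at or below 90%, by oxygen status within age group and cohort, using individual listings where cells are small;
- report by age group and cohort the number of children whose oxygen was newly started or increased after the first dose.

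The cost is one field per reading and a little extra table work. With six children per cohort the split cells will be small, so the gain is mainly in interpreting individual profiles. There is no added procedure, no change to sample size, and no change to when oxygen is given or to any other clinical rule.

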7.1.4. Single-Dose Phase Assessments and Procedures

The following assessments and procedures will be performed during the Single-Dose Phase (see [Table 3](#)) after the baseline assessments have been completed and the subject is dosed. Every effort should be made to collect blood samples at the assigned time intervals relative to the time of administration of study drug:

- Assess and record current pain intensity at 15 and 30 minutes and at 1, 1.5, 2, 4, 6, 8, 12, and 24 hours (or upon ET) after administration of study drug or until the subject requires rescue medication. Assessments must be made by the Investigator, or designee. Pain will be assessed at time of rescue, but no pain assessments will be completed beyond administration of rescue medication.
- Measurement of vital signs at 15 and 30 minutes and at 1, 1.5, 2, 4, 6, 8, 12, and 24 hours (or upon ET) after administration of study drug.
- Assess respiratory (see section [12.2](#)) and neurological function (see section [12.3](#) and [Appendix A](#)) at 15 and 30 minutes and at 1, 1.5, 2, 4, 6, 8, 12, and 24 hours (or upon ET) after administration of study drug. Assessments must be made by the Investigator, or designee.
- Collection of blood samples for pharmacokinetic assessments at 15 and 30 minutes and at 1, 1.5, 2, 4, 6, 8, 12, and 24 hours (or upon ET) after administration of study drug.
- Record food consumption: capture the date and time of each consumption of food as well as what was consumed eg, DAT, DAT-soft, FFs, CFs, water from 1 hour prior to first dose of study drug administration through EOS/ET.
- Record rescue medication: provide rescue medication on an as needed basis for breakthrough pain (BTP). Rescue medication may include opioid-based patient controlled analgesia (PCA) rescue (but must NOT contain oxycodone or oxymorphone) for as long as the PCA device remains in place per SOC. Oral rescue medications will also be allowed during the study, but also must NOT contain oxycodone or oxymorphone.
- Monitor and document AEs/SAEs throughout the study.
- Update and record concomitant medications (including rescue medications).

Subjects will complete the Single-Dose Phase when they complete the EOS assessments and procedures at 24 hours (or upon ET) following initial study drug administration.

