9.8. Randomization and Blinding

This is an open-label, multicenter study that does not require randomization. No blinding will be performed.

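### Threshold respiratory and heart-rate events become AEs only if the investigator chooses, and the safety analysis plans no count of children who crossed a threshold

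*Combined protocol and SAP*

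**What the plan says.** Section 12.2 sets four triggers:

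- oxygen saturation of 90% or lower;
- heart rate at 50% or less of the age norm;
- respiratory rate at 50% or less of the age norm;
- apnea, which may be taken as 15 seconds or more without breathing.

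For saturation and heart rate, "the event will be recorded as an AE at the discretion of the Investigator". For respiratory rate, "the event will be recorded as an AE of respiratory depression at the discretion of the Investigator". For apnea, "Episodes of apnea will be recorded as an AE at the discretion of the Investigator (or an SAE per respective definition". How apnea is looked for is also left open: "Apnea monitoring may be conducted using direct observation and counting, impedance pneumography, or capnography, based on practice at the respective institution". The one unconditional rule in the section is that an opioid antagonist given for respiratory depression is an SAE.

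Monitoring runs as needed throughout, but "Oxygen saturation and heart rate will be recorded at the time of vital sign assessment". In the Single-Dose Phase (section 7.1.4) that means "Measurement of vital signs at 15 and 30 minutes and at 1, 1.5, 2, 4, 6, 8, 12, and 24 hours". In the Multiple-Dose Phase (section 7.1.5) readings fall at 0.5, 1, 1.5 and 2 hours after Dose 1, and from then on only just before each further dose.

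Section 13.5 tabulates recorded AEs by subject. Vital signs and respiratory assessments are to be "summarized by age group, treatment cohort, and study phase for each time point using appropriate descriptive statistics". On masking, section 9.8 says "No blinding will be performed".

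**The concern.** The protocol defines thresholds but never uses them in the analysis. Whether a crossing appears in the AE tables depends on a judgement by someone who knows the dose, at about 20 sites whose practice may differ. If it is not called an AE, its only other planned route into the results is a per-time-point summary of about six children. That summary need not show a single low value, and it cannot show a value that was never recorded.

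Safety and tolerability are part of the primary objective (section 6.1), and section 12.2 itself names respiratory depression as a known effect of opioids. A reader of the study report would want to know how many children at each dose level fell below the protocol's own limits. The planned outputs do not answer that.

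**Working it through.** The documents state no figure for this point, so there is nothing to reproduce. The check compares sections and then adds two illustrations.

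**1. Routes into the reported results**

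- *Crossing at a scheduled time.* The value is recorded and enters the section 13.5 summary for that time point. Section 13.5 names no statistics. Section 13.6, by contrast, names minimum and maximum, but for pharmacokinetic variables only.
- *Crossing between scheduled times.* No value is planned, so the AE or SAE record is the route.
- *Apnea.* No measured value is planned at any time, so again the AE or SAE record is the explicit route.

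**2. How wide the gaps are**

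- Single-Dose Phase: readings at 2, 4, 6, 8, 12 and 24 hours leave gaps of 2, 2, 2, 4 and 12 hours.
- Multiple-Dose Phase, dosing every 4 to 6 hours: the last Dose 1 reading is at 2 hours and the next is just before Dose 2, a gap of 2 to 4 hours. After that each gap is a full dosing interval of 4 to 6 hours, with the reading at its end.

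**3. One low value in a cell of six (invented data)**

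Cell size 6 comes from section 13.1. Take five children at 98% and one at 88% at one time point.

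- Mean = (5 × 98 + 88)/6 = 578/6 = 96.3; SD = 4.1; median = 98; minimum = 88.
- Counted by threshold: 1/6 = 16.7% (exact 95% CI 0.4% to 64%).

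The mean and median do not show the event and the minimum does. Minima per time point still cannot give the number of children affected: a minimum of 88 at 1 hour and again at 2 hours may be one child or two.

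**4. Effect of incomplete recording (assumed rates)**

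Let p be the true share of children who cross a trigger and r the share of those recorded as AEs. With independent children, P(at least one recorded among n) = 1 − (1 − p·r)^n.

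| n | p | r = 1 | r = 0.5 | r = 0.25 |
|---|---|---|---|---|
| 6 | 5% | 26.5% | 14.1% | 7.3% |
| 6 | 10% | 46.9% | 26.5% | 14.1% |
| 6 | 20% | 73.8% | 46.9% | 26.5% |
| 18 | 10% | 85.0% | 60.3% | 36.6% |

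For example, with n = 6, p = 10% and r = 0.5: 1 − 0.95^6 = 26.5%. The row with n = 18 is one age group in one phase with all three cohorts. Neither p nor r is given in the documents; the table shows only how sensitive an AE-based count is to discretion.

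**The case against.** The strongest case on the other side has four parts.

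- **Escalation does not rest on these tables.** A reader might infer that a hidden event could let the dose go up unnoticed. Section 7 does not support that: the external IDMC assesses all individual as well as aggregate safety data before each escalation. This stands, and it confines the point to the reported analysis. The IDMC can review only what is captured, but nothing limits it to section 13.5 summaries.
- **The worst events do not vanish.** Antagonist use for respiratory depression is always an SAE and leads to discontinuation, so it also shows in the disposition table. Apnea meeting the SAE definition is captured. Section 9.6 requires significant toxicity to be reported to the sponsor at once. This stands. The exposure is limited to untreated, non-serious crossings.
- **Section 12.1.2 requires every AE, including observed signs, to be captured.** The discretion in section 12.2 can then be read as judging whether a reading is a true event, much as section 12.1.1 allows for laboratory values. That reading is fair, but the two sections are not reconciled, and neither produces a count of crossings.
- **The plan does not say means only.** Minima may be reported, and in the example above the minimum is 88. This stands as far as it goes: the statistics are unspecified, which is a weaker criticism than saying the event is hidden. A minimum per time point is still not a count of children and says nothing about events between readings.

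It is also true that the open-label design makes differential recording by cohort possible without showing that it occurs, or in which direction.

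**Conclusion.** The point holds in a limited form. Untreated, non-serious crossings of the section 12.2 triggers that the investigator does not call AEs can be missing from the reported safety results. This is most likely between scheduled readings, and above all after Dose 1 in the Multiple-Dose Phase. At scheduled times, whether a low value is visible depends on statistics that section 13.5 does not name.

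The documents do not support the stronger inferences that serious respiratory depression would go unreported, that dose escalation would be misled, or that such events will be lost as opposed to may be lost.

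The size cannot be fixed from the documents. On an assumed 10% crossing rate with half recorded, the chance of seeing any event in a cell of six is 26.5% against 46.9% with full counting; other assumed rates give the range in the table. The conclusion itself rests only on the text of sections 7.1.4, 7.1.5, 12.2 and 13.5. The change is a cheap improvement to a primary-objective safety result, not the repair of a fatal flaw.

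**What to change.** In section 13.5, add the following by age group, cohort and phase, irrespective of AE status:

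- the number and percentage of children with any post-dose saturation of 90% or lower;
- each child's lowest post-dose saturation, heart rate and respiratory rate;
- a by-subject listing of these values;
- the same counts for the heart-rate and respiratory-rate triggers, using one pre-specified age-norm reference table, since section 12.2 gives none.

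On the eCRF, record crossings seen between scheduled times. Report apnea as observed, with the site's monitoring method noted, because counts will otherwise reflect how hard each site looked. Reconcile the discretion in section 12.2 with the capture rule in section 12.1.2.

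The cost is one extra table and listing, a short eCRF line and a fixed age-norm reference. The saturation count and lowest values at scheduled times use data already collected; the other items need the reference table or the eCRF line. No dose, monitoring or treatment rule changes.
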